6.3.2 Static Investigator's Global Assessment (static IGA)

The static IGA^[15] is used to measure psoriasis severity in clinical trials. The static IGA used in this trial will be a 6-point scale and will be evaluated at the time points indicated in the schedule of events (Table 1). The scoring is based on response to treatment measured by lesion erythema, induration, and scale. The static IGA scoring and descriptors are as follows:

LYC-30937

Clinical Protocol LYC-30937-2003

Issue Date: 30 August 2016

Score	Short Descriptor	Detailed descriptor
0	Cleared	No plaque elevation, erythema or scaling; hyperpigmentation may be present
1	Minimal	Minimal plaque elevation (=0.25mm); faint erythema; minimal scaling, with occasional fine scale over < 5% of lesion
2	Mild	Mild plaque elevation (=0.5mm); light red coloration; fine scale predominates
3	Moderate	Moderate plaque elevation (=0.75mm); moderate red coloration; coarse scale predominates
4	Marked	Moderate plaque elevation (=1mm); bright red coloration; thick, non-tenacious scale predominates
5	Severe	Severe plaque elevation (≥ 1.25 mm); dusky to deep red coloration; very thick, tenacious scale predominates

6.4 Safety Assessments Performed

6.4.1 Physical Examinations (PE)

A standard PE will be performed by the PI or by an appropriately trained individual at the time points indicated in the schedule of events (Table 1) and will include a review of body systems outlined below.

- general appearance
- head, eyes, ears, nose, and throat (HEENT)
- respiratory examination

LYC-30937

Clinical Protocol LYC-30937-2003

Issue Date: 30 August 2016

- circulatory system
- abdominal examination
- musculoskeletal
- neurological examination (to record the presence of abnormalities in mental status, motor, and sensory function [includes reflexes])
- any additional assessments necessary to establish baseline status or evaluate symptoms or adverse experiences

Every effort should be made to have the same examiner perform each PE for a given subject to minimize variability in the examinations. Clinically significant changes from screening should be noted as AEs.

6.4.2 Vital Signs Measurements

Vital signs measurements will be performed at the time points indicated in the schedule of assessments (Table 1) and will consist of BP (systolic and diastolic), HR, RR, and temperature. Subjects should sit quietly with feet flat on the floor or be supine (lying down) for at least 5 minutes prior to measurements.

- Subject must remain seated or lying down for the entire measurement.
- The use of automated devices for measuring BP and HR is acceptable. If done manually, HR must be measured in the brachial/radial artery as per site standard procedures.
- Blood pressure determinations must be performed using calibrated and appropriately maintained equipment and the same equipment should be used on the same subject throughout the study as much as possible.
- The same size BP cuff, which has been properly sized and calibrated, will be used to measure BP each time.

Subject's arm should be at the same height (at the level of the heart) during each BP measurement. Clinically significant changes from baseline should be recorded as AEs.

LYC-30937

Clinical Protocol LYC-30937-2003

Issue Date: 30 August 2016

6.4.3 12-Lead ECG

A standard 12-Lead ECG will be performed after 5 minutes of rest in the supine position using a standardized automated device at the time points indicated in the schedule of assessments (Table 1). The following ECG parameters will be recorded: HR, PR-interval, QRS-duration, QT-interval, QT interval corrected for HR according to Fridericia's formula (QTcF)-interval and the PI's assessment of the ECG profile. Clinically significant changes from screening should be recorded as AEs.

6.4.4 Laboratory Assessments

Laboratory assessments will be performed at the time points indicated in the schedule of assessments (Table 1) and will be evaluated by a central laboratory.

The PI at the site must assess the clinical significance of all laboratory values outside the laboratory reference ranges. All laboratory abnormalities considered to be clinically significant by the PI should be repeated. Confirmed, clinically significant laboratory abnormalities should be further evaluated by the PI and captured as an AE.

Chemistry Panel Sample

The chemistry panel includes: glucose, calcium, sodium, albumin, total protein, potassium, bicarbonate, chloride, blood urea nitrogen (BUN), creatinine, lactate, lactate dehydrogenase (LDH), alanine aminotransferase (ALT), aspartate aminotransferase (AST), reflexive bilirubin (total, direct, indirect), alkaline phosphatase (ALP), cholesterol, triglycerides, creatine phosphokinase (CPK), high sensitivity C-reactive protein (hsCRP), high density lipoprotein (HDL), and low density lipoprotein (LDL).

Hematology Panel Sample

The hematology panel includes: platelets, WBCs with differential if abnormal (% and absolute counts), hematocrit, red blood cells (RBCs), hemoglobin, mean corpuscular volume (MCV), mean corpuscular hemoglobin concentration (MCHC), and mean corpuscular hemoglobin (MCH).

LYC-30937

Clinical Protocol LYC-30937-2003

Issue Date: 30 August 2016

Urine Sample (Dipstick)

The urinalysis test includes: color, appearance, specific gravity, leukocyte esterase, pH, protein, glucose, ketones, blood, and nitrates. Microscopic urinalysis will be performed on samples with abnormal blood, leukocyte esterase, protein, and nitrate. This test will be evaluated by dipstick at the central laboratory.

Childbearing Potential Evaluation and Pregnancy Tests

Serum FSH in postmenopausal female subjects and a serum hCG (pregnancy test) in premenopausal females will be evaluated at the central lab at screening.

Urine pregnancy tests for female subjects of childbearing potential will be performed at the time points indicated in the schedule of assessments (Table 1).

6.4.5 Body Temperature monitoring

Subjects' body temperature will be measured at clinic visits (Table 1). Use the same type thermometer throughout the study (eg, oral, axillary, etc.)

If the temperature reading is $> 101^{\circ}\text{F}$ (or 38.3°C), the subject is to be evaluated for a possible bacterial or viral infection. This assessment is to be completed per the investigator's best clinical judgment (eg, if there is suspicion of a urinary tract infection, then the subject is to have a urinalysis performed; if the subject has signs and symptoms of a classic viral upper respiratory tract infection, then the subject can be treated symptomatically without being evaluated).

If there are no signs or symptoms of infection, the study drug is to be withheld and the subject should be evaluated for other sources of increased temperature as medically indicated. Study drug may be re-started if it has not been interrupted for more than 3 days and the source of the elevated temperature is determined, or it resolves, and in the clinical judgement of the investigator and study medical monitor it is safe for the subject to continue study drug. If the subject is off study drug for more than 3 days the investigator should withdraw the subject from the trial.

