2.3.3 Safety Pharmacology and Toxicology

LYC-30937 is not genotoxic and does not produce adverse central nervous system (CNS), pulmonary or cardiovascular effects in single dose safety pharmacology studies. In rats and monkeys dosed for up to 28 days with LYC-30937, there was no evidence of generalized immunosuppression.

In the rat 28-day good laboratory practice (GLP) toxicology study, an AUC of ≥ 5800 ng·h/mL was associated with sporadic instances of mortality. The NOAEL was 2 mg/kg/day with plasma AUC values of 1690 ng·h/mL in male rats and 1040 ng·h/mL in female rats. In the rat 91-day GLP toxicology study, the no observed adverse event level (NOAEL) was 10 mg/kg with a plasma AUC of 7750 ng·h/mL (combined sex mean). Since mortality was observed in previous studies at a lower AUC, the rat NOAEL across all studies was considered to be the mid dose in the 91-day of 3 mg/kg with a C_{max} of 257 ng/mL and an AUC of 3060 ng·h/mL.

LYC-30937

Clinical Protocol LYC-30937-2003

Issue Date: 30 August 2016

Due to the mitochondrial mechanism of action of LYC-30937, a study was conducted to explore uncoupling as a potential cause of mortality in rats at high plasma drug levels. As measured by indirect calorimetry, at doses ≥ 7 mg/kg, LYC-30937 produced dose-related increases in oxygen consumption and body temperature consistent with mitochondrial uncoupling. At a tolerated dose, measurable and reversible increases were observed for both parameters.

In the 28-day GLP monkey toxicology study, an exposure of 6340 ng·h/mL in the male high dose group (30 mg/kg) was associated with dose-limiting emesis and diarrhea leading to euthanasia of the group following 16-18 days of dosing. In surviving animals, complete recovery from these clinical signs occurred following a reversal period of 28 to 38 days. The NOAEL in the 28-day monkey study was 10 mg/kg/day associated with an AUC of 4820 ng·h/mL (combined sex mean). In the 91-day GLP toxicology study, the NOAEL was 10 mg/kg with an AUC of 2580 ng·h/mL.

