6.4.6 Monitoring Subjects for Adverse Events of Special Interest

Subjects will be monitored throughout the study for the occurrence of AEs and for abnormal clinical laboratory values.

LYC-30937

Clinical Protocol LYC-30937-2003

Issue Date: 30 August 2016

AEs of special interest include those that may be related to LYC-30937's mechanism of action of mitochondrial modulation and those AEs which may indicate hepatotoxicity. Investigators should be particularly mindful of these AEs, which include vomiting, abdominal pain, elevated lactate, and abnormal liver function tests indicative of possible hepatotoxicity (AST, ALT, total bilirubin, ALP, LDH). Guidance for monitoring for these AEs of special interest is outlined below:

Vomiting or Abdominal Pain:

If a subject exhibits repeated episodes of vomiting or persistent abdominal pain they must contact their investigator. They should present to the clinic as soon as possible to be evaluated for potential source of the symptom and liver function testing should be performed. The study medical monitor should be contacted. If a source is not readily identified then study drug should be withheld and the subject should continue to be evaluated for the source and managed as medically indicated. Study drug may be re-started if it has been interrupted for no more than 3 days and the source of the vomiting or abdominal pain is determined, or if these symptoms resolve, and in the clinical judgement of the investigator and study medical monitor it is safe for the subject to continue study drug. If the subject is off drug for more than 3 days the investigator should withdraw the subject from the study.

Monitoring Lactate and Liver Function:

If a subject exhibits any of the following elevations, study drug should be withheld at least until evaluation of the subject:

- ALT or AST > 8 x ULN
- ALT or AST > 5 x ULN for more than 2 weeks
- ALT or AST > 3 x ULN and total bilirubin > 2 x ULN
- ALT or AST > 3 x ULN with appearance of fatigue, nausea, vomiting, right upper quadrant pain or tenderness, fever, rash and/or eosinophilia (> 5%)
- ALP > 1.5 x ULN
- Lactate \geq 3 mmol/L
- LDH > 2 x ULN

If any of the above occur the investigator must contact the subject to request the stop taking study drug and report to the clinic as soon as possible for evaluation (do not wait for the next

LYC-30937

Clinical Protocol LYC-30937-2003

Issue Date: 30 August 2016

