scheduled study visit). As dehydration and heavy physical exertion can cause elevations (eg, of blood lactate levels), the clinical lab should be repeated with the subject instructed to ensure hydration and avoid heavy physical activity. The study medical monitor should be contacted to discuss the case. If the elevation is confirmed by repeat lab and neither dehydration nor physical exertion explains the elevation, study drug must continue to be withheld. Close observation of the subject should be initiated. Repeat liver enzyme and serum bilirubin testing should be performed 2 to 3 times weekly until values return to baseline. Frequency of this retesting can decrease to once per week or less if abnormalities stabilize or the study drug has been discontinued and the subject is asymptomatic. The investigator should obtain a detailed history of symptoms, prior or concurrent diseases, concomitant drug use, alcohol use, recreational drug use, special diets, and exposure to environmental chemical agents. Evaluation should be performed to rule out acute viral hepatitis types A, B, C, D and E; autoimmune or alcoholic hepatitis; nonalcoholic steatohepatitis; hypoxic/ischemic hepatopathy; and biliary tract disease. Obtain additional tests to evaluate liver function as appropriate (eg, international normalized ratio, direct bilirubin). Consider gastroenterology or hepatology consults. If a source of the abnormal value is not readily identified the subject should continue to be evaluated for the source and managed as medically indicated. Study drug may be re-started if study drug has been interrupted for no more than 3 days and the source of the abnormal value(s) is determined, or if upon repeating the clinical lab the value returns to normal, and in the clinical judgement of the investigator and study medical monitor it is safe for the subject to continue study drug. If study drug cannot be ruled out as the cause of the abnormal value then study drug should be permanently discontinued. Additionally, if study drug is interrupted for more than 3 days, then study drug should be permanently discontinued.

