5.6 Visit Windows

Data at scheduled visits will be assigned to analysis visits as defined in the Visit Window table below. To ensure that all visits have the possibility to be included in the summaries, the visit window will also classify all unscheduled and early termination visits. The analysis visits will be derived in terms of study days since the first dose of study

treatment for safety assessments, or since the date of randomization for efficacy assessments. These analysis visits will be utilized in the summary and analyses of efficacy and safety endpoints.

If a subject has more than 1 assessment in a visit window, only the assessment that is closest to the Scheduled Visit Day will be used for analysis. In case 2 assessments have the same distance from the Scheduled Day, the later assessment will be used for analysis. The early termination visit will be assigned to an analysis visit based on the window below.

Separate visit window tables are provided based on how frequently the assessments were done. For assessment which has only 1 scheduled post-baseline assessment, say at Week 12, Scheduled Visit Day will be similar as either of the tables below with visit window upper limit of Day 92, and all previous rules will apply.

No visit windows will be applied for summaries of the follow-up period data.

Table 1 Visit Windows for Assessments Done at Baseline and Weeks 2, 4, 8, and 12

Analysis Visit	Scheduled Visit Day	Visit Window for Summarization
Baseline	Day 1	≤ Day1
Week 2	Day 15	Day 2 – Day 22
Week 4	Day 29	Day 23 – Day 43
Week 8	Day 57	Day 44 – Day 71
Week 12	Day 85	Day 72 – Day 92

Table 2 Visit Windows for Assessments Done at Baseline and Weeks 4, 8, and 12

Analysis Visit	Scheduled Visit Day	Visit Window for Summarization
Baseline	Day 1	≤ Day1
Week 4	Day 29	Day 2 – Day 43
Week 8	Day 57	Day 44 – Day 71
Week 12	Day 85	Day 72 – Day 92

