5.7 Handling of Missing Data

Missing data will be handled differently depending on the parameter and analysis:

- No imputation for missing values will be applied for PASI and static IGA response variables. The summaries will be based on observed cases only.

- Missing baseline values will not be imputed in any situation.
- Post-baseline values for by-visit data will be summarized and/or analyzed using the Visit Windows from Section 5.6. If a value is not available within a given window, no imputation will be done.
- Missing data for AE relationship will be imputed as “Related.”
- Refer to Appendix 3 for details of imputing partial dates for AE, when applicable.
- Refer to Appendix 4 for details of imputing partial dates for prior and concomitant medication, when applicable.

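### After more than 3 days off drug, two rules withdraw the subject and a third only stops drug; withdrawal before Day 72 can remove the subject from the Week 12 primary analysis

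*Protocol*

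**What the plan says.** Three rules in the protocol turn on more than 3 days off drug.

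- **Raised temperature without signs of infection (Protocol 6.4.5):** "If the subject is off study drug for more than 3 days the investigator should withdraw the subject from the trial".
- **Repeated vomiting or persistent abdominal pain (Protocol 6.4.6):** "If the subject is off drug for more than 3 days the investigator should withdraw the subject from the study".
- **Lactate or liver test elevations (Protocol 6.4.6):** "if study drug is interrupted for more than 3 days, then study drug should be permanently discontinued". This part does not say whether the subject leaves the study or whether efficacy visits go on.

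Protocol 4.5 asks a withdrawn subject to have the Visit 6/Week 12 procedures if possible, and Table 1 gives Week 12 and early termination one shared column. Nothing asks for a PASI after that visit. Protocol 4.5 also lets the sponsor replace withdrawn subjects case by case.

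On the analysis side, SAP 4.1 defines the FAS as all randomized subjects and runs every efficacy analysis on it. SAP 5.6 says: "The early termination visit will be assigned to an analysis visit based on the window below". For PASI (SAP Table 2), Days 2 to 43 count as Week 4, Days 44 to 71 as Week 8 and Days 72 to 92 as Week 12. SAP 5.7 does not impute PASI or static IGA response: "The summaries will be based on observed cases only". The primary test in SAP 6.1 is an ANCOVA on the Week 12 percent change, and no sensitivity analysis for missing values is given there or in 5.7.

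**The concern.** There are two linked problems.

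First, the protocol is unclear about what follows an interruption of more than 3 days. Sites could continue visits for one subject and end them for another. One subject can also fall under two rules. The vomiting rule calls for liver function testing, and the laboratory list includes a transaminase elevation accompanied by vomiting or fever. Such a subject would be withdrawn under one rule and only taken off drug under the other.

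Second, withdrawal can end PASI collection before the primary time point, and the analysis then leaves the subject out. For that test, all randomized subjects becomes all subjects with a PASI on Days 72 to 92. The secondary Week 12 endpoints depend on the same visit.

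The loss may not be random. Of the special-interest list, which includes vomiting and abdominal pain, the protocol says: "AEs of special interest include those that may be related to LYC-30937's mechanism of action of mitochondrial modulation". Temperature is not on that list, but the rat work in Protocol 2.3.3 found that "LYC-30937 produced dose-related increases in oxygen consumption and body temperature consistent with mitochondrial uncoupling". If such events were commoner on active drug, and the affected subjects would have done worse than those retained, the observed-case comparison would flatter the drug. With 20 active subjects, each one lost is 5% of the arm.

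**Working it through.** **Path of a withdrawn subject.** Take an early termination PASI before Day 72 with no later PASI.

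1. SAP Table 2 assigns it to Week 4 (up to Day 43) or Week 8 (Days 44 to 71).
2. The Week 12 window is empty, and SAP 5.7 does not fill it.
3. The percent change at Week 12 does not exist, so the subject is not in the ANCOVA.

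A PASI on Days 72 to 92 still counts, whether from a late termination visit or from a return visit. The subject remains in the FAS by definition; the loss comes from the windows and the observed-case rule.

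**Inputs (Protocol 8.1, repeated in SAP 5.2).** There are 20 active and 10 placebo subjects. Mean PASI improvement is 52.7% on active and 16.7% on placebo, the common SD is 32.0, and the test is a two-sided t-test at 0.05. Improvements are written here as positive numbers, as in that section.

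**The plan's own figure.** Standard error = 32.0 × √(1/20 + 1/10) = 12.39. Noncentrality = 36.0 / 12.39 = 2.905. With 28 degrees of freedom the critical value is 2.048, and the noncentral t distribution gives power of 80.1%. The stated value of about 80% is reproduced. It needs all 30 subjects to be evaluable; no allowance for dropout is stated.

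**Illustration.** The documents give no rate for these withdrawals, so k = 1 to 4 lost active subjects is an assumption. The subjects who remain are assumed to average 52.7%, no placebo subject is lost, and the observed-case difference is therefore 52.7 − 16.7 = 36.0 throughout. If the lost subjects would have averaged m at Week 12:

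all-randomized difference = [(20 − k) × 52.7 + k × m] / 20 − 16.7

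Two values of m are shown: the placebo mean (16.7) and no change (0). For k = 2 and m = 16.7 this is (948.6 + 33.4)/20 − 16.7 = 49.1 − 16.7 = 32.4. Power uses the same noncentral t calculation with 20 − k and 10 subjects and a difference of 36.0.

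| Active subjects lost | Observed-case difference | All-randomized, m = 16.7 (excess) | All-randomized, m = 0 (excess) | Power |
|---|---|---|---|---|
| 0 | 36.0 | 36.0 | 36.0 | 80.1% |
| 1 | 36.0 | 34.2 (1.8) | 33.4 (2.6) | 79.3% |
| 2 | 36.0 | 32.4 (3.6) | 30.7 (5.3) | 78.4% |
| 3 | 36.0 | 30.6 (5.4) | 28.1 (7.9) | 77.4% |
| 4 | 36.0 | 28.8 (7.2) | 25.5 (10.5) | 76.4% |

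The excess is the amount by which the observed-case difference overstates the all-randomized one.

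**The case against.** The three rules concern different events and share only the 3-day limit. Different events may deserve different rules, and the laboratory part needs frequent retesting, which may be why it does not order withdrawal. This has force: the text is non-uniform and incomplete rather than flatly contradictory. It does not settle what happens to a subject who meets two rules, nor whether visits continue under the laboratory rule.

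The documents also give little reason to think such events will be frequent. In Phase 1a (Protocol 2.4) all treatment-emergent events were mild, none led to discontinuation, and vital signs including temperature showed nothing clinically significant. Projected fasted exposure is more than 70-fold below the rat no-effect level (Protocol 2.5). Against that, repeat dosing lasted 7 days there and lasts 84 days here. The rate is unknown, which is why the working shows a range.

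Several stronger readings are tempting but not supported:

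- A reader might infer that lactate and liver elevations also force subjects out. That rule orders only the end of study drug.
- A reader might infer that the sponsor expects these events. The protocol says only that some may be related to the mechanism.
- A reader might quote the power for 18 and 9 subjects (75.5%) or 16 and 8 (70.0%). Those describe equal proportional loss in both arms, which is general dropout and not a consequence of these rules.
- A reader might conclude that withdrawal is unnecessary once drug is stopped. That is a clinical judgement and is not made here.

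Finally, replacement under Protocol 4.5 could restore the count and so the power. It cannot restore the outcomes of the subjects who left.

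**Conclusion.** The point holds in a limited form. The passages on more than 3 days off drug need reconciling, whatever the event rate. Two of them end participation, and the SAP then leaves a subject without a PASI on Days 72 to 92 out of a primary analysis described as covering all randomized subjects.

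Possible bias matters more than lost power. With 1 to 4 active subjects lost, the observed-case difference would overstate the all-randomized one by 1.8 to 7.2 points if they would have matched placebo, or by 2.6 to 10.5 points if they would not have changed. Power would fall by 0.8 to 3.7 points from 80.1%, before any replacement. These sizes rest on assumed numbers of lost subjects, all from the active arm, and on assumed outcomes for them. That the loss differs by arm is plausible but not shown, and that it favours active drug is an inference.

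**What to change.** 1. **Reconcile the three passages.** The sponsor should align Protocol 6.4.5 with the two parts of 6.4.6, and state separately when a subject stops study drug and when a subject leaves the study. No view is taken on which clinical rule is right.
2. **Add a data-collection provision.** Unless consent is withdrawn, ask subjects who stop drug to attend the remaining scheduled Week 4, 8 and 12 PASI, BSA and static IGA assessments. Use the Week 12 value in the FAS analysis, under the arm to which the subject was randomized. Record any psoriasis therapy started after drug is stopped.
3. **Add a sensitivity analysis to the SAP** for Week 12 PASI values that are still missing. The two assumptions in the working, placebo-like outcome and no change, are natural choices.

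The cost is protocol and SAP wording and a few more attended visits, all already in the schedule. The main drawback is that some Week 12 values will come from subjects off drug and may be affected by other therapy, which is why that therapy has to be recorded. Missing values from other causes of withdrawal will remain, and item 3 covers them too.
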